## APPENDIX C AMENDMENTS AND ADMINISTRATIVE CHANGES TO THE PROTOCOL

GlaxoSmithKline Biologicals SA	
Vaccines R &D	
Protocol Amendment 1	
eTrack study number and Abbreviated Title	205847 (TBEV POLYGELINE FREE-025 EXT:021)
EudraCT number	2017-001356-59
Amendment number:	Amendment 1
Amendment date:	25 August 2017
Co-ordinating author:	PPD, Scientific writer, contractor for GSK Biologicals
Rationale/background for changes:	
Following feedback from CA and EC, this protocol has been amended to provide clarifications about:	

 
• End of study (EoS): this can be either the last Visit due for “immune persistence” evaluation (V27) or last Visit due for the “boostability” evaluation in case of subresponder(s) to be re-vaccinated (V27.2).
 
• Duration of the study: “less of 5 years” is now used consistently throughout the protocol and with the ICF.
 
	

**Amended text has been included in *bold italics* and deleted text in ~~strikethrough~~ in the following sections:**

The following statement in the copyright statement has been deleted as it is not relevant (new copyright statement is in place):

~~Unauthorised copying or use of this information is prohibited.~~

### **In Synopsis, Study design and Section 3 Study design overview:**

- Duration of the study: For each subject, the study will last ~~approximately less than 5~~ years.
  - Epoch 001: Persistence evaluation starting at Visit 23 (Year 11) and ending at ***Visit 27 or*** Visit 27.2.
- End of Study (EoS): Last testing results released of samples collected at ***Visit 27 or*** Visit 27.2.

#### Rationale/background for changes:

##### This protocol has been amended to clarify that:

- New subject identification numbers will be assigned in the study with an established link to the subject identification numbers used in the previous V48P7, V48P7E1 and V48P7E2 studies
- Despite there being no randomization in the study; Source DataBase for Internet Randomization (SBIR) is being used for allocation of the study treatment and management of study vaccines.

Additionally, the exact assay name and details of the TBE-neutralization test has been presented.

**Amended text has been included in *bold italics* and deleted text in ~~strikethrough~~ in the following sections:**

#### In Section 5.2 Subject identification and randomisation:

The subjects will have the same identification numbers as the previous studies. *The subjects will have new identification numbers which will be pre-assigned with a link established to the subject identification numbers used in the previous V48P7, V48P7E1 and V48P7E2 studies.* There is no randomization in the study as only the number of subjects who will have a NT antibody titre of below 10 will receive vaccination.

*However allocation of the study treatment and management of study vaccines will be done through Source DataBase for Internet Randomization (SBIR).*

#### In Section 5.2.1 Treatment allocation to the subject (who may receive vaccination in the study)

The treatment numbers will be allocated by product.

After obtaining the signed and dated ICF from the subject and having checked the eligibility of the subject, the site staff in charge of the vaccine administration will ~~take, access SBIR~~ at Visit 23.1/ Visit 24.1/ Visit 25.1/ Visit 26.1/ Visit 27.1. ~~the lowest treatment number for the vaccine dose to be used for the subject. Upon providing the subject identification number, the randomisation system will provide the treatment number to be used for the dose.~~

The number of the administered treatment must be recorded in the eCRF on the Vaccine Administration screen.

*When SBIR is not available, please refer to the SBIR user guide or the Study Procedures Manual for specific instructions.*

**In Section 5.6 Detailed description of study procedures; sub section 5.6.16 Study group and treatment number allocation**

Not applicable.

*Study group and treatment number allocation will be performed as described in Section 5.2. The number of the administered treatment must be recorded in the eCRF.*

**In Section 5.7.3 Laboratory assays**

**Table 8      Humoral Immunity (Antibody determination)**

System	Component	Method	Kit / Manufacturer	Unit*	Cut-off*	Laboratory**
Serum	Anti TBE Antibody	NT	GSK Biologicals***	- 1/dilution	4:2 2	GSK Biologicals***

\* Assay cut-off and unit might be subject to change during the course of the study (e.g. in case of requalification, revalidation or standardization). In this case, this will be documented in the clinical report.

\*\*Refer to APPENDIX B for the laboratory addresses.

\*\*\* GSK Biologicals laboratory refers to the Clinical Laboratory Sciences (CLS) in Rixensart, Belgium; Wavre, Belgium; Marburg, Germany

**In Section 5.7.4.1 Immunological read-outs****Table 9      Immunological read-outs**

Blood sampling timepoint		Subset /Sub-cohort Name	No. subjects	Component	Components priority rank
Type of contact and timepoint	Sampling timepoint				
Visit 23	Year 11	All subjects	200	Anti TBE Antibody *	1
Visit 23.2	Year 11 + 6 months + 21 days	Subjects with second booster on Visit 23.1**	**	Anti TBE Antibody *	1
Visit 24	Year 12	All subjects	200	Anti TBE Antibody *	1
Visit 24.2	Year 12 + 6 months + 21 days	Subjects with second booster on Visit 24.1**	**	Anti TBE Antibody *	1
Visit 25	Year 13	All subjects	200	Anti TBE Antibody *	1
Visit 25.2	Year 13 + 6 months + 21 days	Subjects with second booster on Visit 25.1**	**	Anti TBE Antibody *	1
Visit 26	Year 14	All subjects	200	Anti TBE Antibody *	1
Visit 26.2	Year 14 + 6 months + 21 days	Subjects with second booster on Visit 26.1**	**	Anti TBE Antibody *	1
Visit 27	Year 15	All subjects	200	Anti TBE Antibody *	1
Visit 27.2	Year 15 + 6 months + 21 days	Subjects with second booster on Visit 27.1**	**	Anti TBE Antibody *	1

\*The results of this testing might potentially impact the subject medical care.

\*\*Only subject with an NT antibody titre below 10 at a scheduled visit will receive 6 months later a second booster vaccination and will have an additional blood draw 21 days after this vaccination.

1. DOCUMENT HISTORY

Date	Description	Protocol Version
04-SEP-2017	Final version	Final – 25-AUG-2017

2. STUDY DESIGN

The study design of the current study along with the past 2 studies (primary and booster) is presented in the figures below. [Figure 1](#) presents the primary study, [Figure 2](#) presents booster study and [Figure 3](#) presents the current long term follow-up study.

Figure 1 Study design of Studies V48P7

[figure not shown]
C = Conventional schedule; **R** = Rapid schedule; **AC** = Accelerated Conventional schedule; **MC** = Modified Conventional schedule; **Rando** = randomisation; **LV**= Last Visit; **V** = Visit; **D** = Day; **VAC1**, **VAC2**, **VAC3** = vaccination 1, 2 or 3 (indicated in grey);

CONFIDENTIAL

205847 (TBEV POLYGELINE FREE-025 EXT:021)

Statistical Analysis Plan Final

Figure 2 Study design of study V48P7E1 and TBEV Polygeline-free-023 Ext:021 (V48P7E2)

[figure not shown]

TBE_R_B = R-schedule in V48P7 and Booster before enrollment in V48P7E1; **TBE_R** = R-schedule in V48P7 and Booster in V48P7E1; **TBE_C** = C-schedule in V48P7 and Booster in V48P7E1; **TBE_AC** = AC-schedule in V48P7 and Booster in V48P7E1; **TBE_MC** = MC-schedule in V48P7 and Booster in V48P7E1; **C** = Conventional schedule in study V48P7; **R** = Rapid schedule study V48P7; **AC** = Accelerated Conventional schedule study V48P7; **Enrol** = Enrolment; **LV** = Last Visit; **V** = Visit; **D** = Day; **Y** = Year; **BVAC** = Booster Vaccination; **BS** = Blood Sample

*Booster vaccination 3 years after primary vaccination in V48P7, except TBE R-B (vaccination before enrolment in V48P7E1 and BS only on Day 0)

Study group MC was not followed, it is not a registered schedule; *last V48P7E1 visit is screening visit

Figure 3 Study design of TBEV Polygeline-free-025 Ext:021

TBEV POLYGELINE FREE-025 EXT:021 (205847)

C = Conventional schedule in study V48P7; **R** = Rapid schedule study V48P7; **AC** = Accelerated Conventional schedule study V48P7; **Enrol** = Enrolment; **VAC**=Vaccination; **LV**= Last Visit; **V** = Visit; **D** = Day; **Y** = Year; **BS** = Blood Sample; **SF** = safety follow-up

* Approximate number of subjects planned for persistency, number of subjects with a NT titre below 10 during the study cannot be estimated.

**Some or all of these visits may not be needed, depending on necessary booster vaccination of subjects.

Protocol waivers or exemptions are not allowed unless necessary for the management of immediate safety concerns. Therefore, adherence to the study design requirements, including those specified in the outline of study procedures (Section 5.5 of 205847 “TBEV POLYGELINE FREE-025 EXT:021” protocol Amendment 1 Final: 25 August 2017), are essential and required for study conduct.

- Experimental design: Phase IV, open-label, mono-centric study.
- Duration of the study: For each subject, the study will last less than 5 years.
 - Epoch 001: Persistence evaluation starting at Visit 23 (Year 11) and ending at Visit 27 or Visit 27.2.
- Primary completion Date (PCD): Visit 27.
- End of Study (EoS): Last testing results released of samples collected at Visit 27 or Visit 27.2.
- Study groups: Same groups as in study TBEV POLYGELINE FREE (V48)-023EXT:021

3. OBJECTIVES

3.1. Primary objective

- To evaluate the persistence of antibody response to a booster dose of *Encepur Adults* vaccine starting ≥ 11 years after the first booster administration and to continue following subjects up to 15 years after first booster administration.

3.2. Secondary objectives

- To evaluate the immune response at 21 days after the second booster dose (boostability) in subjects with an NT titre below 10.
- To evaluate the safety of a second booster dose with regard to SAEs collected after vaccination until study end.

4. ENDPOINTS

4.1. Primary Endpoints

The immunogenicity endpoints will be based on the TBE NT antibody levels in serum at year 11, 12, 13, 14 and 15 as measured by GSK Biologicals' NT.

Measures of immunogenicity are:

- Percentages of subjects with detectable TBE Neutralizing Antibody Titres ≥ 2 and ≥ 10 as measured by GSK Biologicals' NT.
- Geometric Mean Antibody Titres as measured by GSK Biologicals' NT calculated for each of the different schedule groups.

Endpoints will be summarized according to the immunization schedule received in the V48P7 study and further detailed by the following age subgroups: 25 to 49 years, ≥ 50 years and ≥ 60 years.

4.2. Secondary Endpoints

The immunogenicity endpoints for subjects who received a second booster vaccination will be based on the TBE NT antibody levels in serum at 21 days after the booster vaccination as measured by GSK Biologicals' NT.

Measures of immunogenicity are:

- Percentages of subjects with detectable TBE Neutralizing Antibody Titres ≥ 2 and ≥ 10 as measured by GSK Biologicals' NT, overall and by study group.
- Geometric Mean Antibody Titres and Geometric Mean Ratios (GMRs) blood draw after/before booster as measured by GSK Biologicals' NT, overall and by study group.
- To complement the analysis of persistence, a thorough description of NT waning from year 1 after the first booster dose up to 15 years will be presented for the set of subjects completing the entire 15-year follow-up with no protocol deviations, including those receiving a second booster dose within the previous clinical studies and current study; for those ones, a constant value of NT = 1 from the post booster visit will be used in the analysis. To this end, percentages of subjects with detectable TBE Neutralizing Antibody Titres ≥ 2 and ≥ 10 and GMTs will be presented by study group.

Endpoints will be summarized according to the primary immunization schedule received in the parent study (V48P7).

The safety endpoint for subjects who will need a second booster vaccination will be based on SAEs collection after the administration of the booster dose. In vaccinated subjects all SAEs will be collected for 1 month after vaccination. Depending on the timing of the booster dose this will be in the period year 11.5 (Visit 23.1), 12.5 (Visit 24.1), 13.5 (Visit 25.1), or 14.5 (Visit 26.1) or from year 15.5 (Visit 27.1) until 21 days after year 15.5 (Visit 27.2). Post-study SAEs will be collected until study conclusion (Refer Section 8.3.2 of 205847 “TBEV POLYGELINE FREE-025 EXT:021” protocol Amendment 1 Final: 25 August 2017 for details on post-study SAEs)

Measures of safety are:

- Incidence of serious adverse events.

5. ANALYSIS SETS

5.1. Definition

Definition of populations:

- a. All Enrolled Population
- all subjects who:
have signed an informed consent and have been enrolled
- b. Full Analysis Set-1 (FAS-1)/Modified Intention-to-treat-1 (MITT-1) population, Immunogenicity
- all subjects in the enrolled population who:
provide at least one evaluable serum sample
- c. Full Analysis Set-2 (FAS-2)/Modified Intention-to-treat (MITT) population, Immunogenicity
- all subjects in the enrolled population who receive one booster dose during the trial and provide one evaluable serum sample after booster dose
- d. Per Protocol Set/ Per protocol-1 (PP-1) population, Immunogenicity
- all subjects in the FAS-1/MITT-1 Immunogenicity population who:
provide evaluable serum samples at the relevant time points and have no major protocol violation as defined in the Statistical Analysis Plan (SAP).
- e. Per Protocol Set/ Per protocol-2 (PP-2) population, Immunogenicity
- all subjects in the FAS-2/MITT-2 Immunogenicity population who:
provide evaluable serum samples after booster dose and have no major protocol violation as defined in the Statistical Analysis Plan (SAP).

A major deviation is defined as a protocol deviation that is considered to have a significant impact on the immunogenicity result of the subject.

Examples of major deviations would include:

- confirmed exposure to TBEV (documented diagnosis of TBEV infection) or other Flaviviruses,
- documented TBEV or *Flavivirus* vaccination other than indicated during the course of the study.

The main populations for immunogenicity analyses will be the PPS. FAS will be supplied as sensitivity analyses.

f. Safety Population

- The safety population will include all subjects who will receive a booster vaccination in this study.

5.2. Criteria for eliminating data from Analysis Sets

Elimination codes are used to identify subjects to be eliminated from analysis. Detail is provided below for each sets.

5.2.1. Elimination from Exposed Set (ES)

Not applicable.

5.2.2. Elimination from Per-protocol analysis Set (PPS)

5.2.2.1. Excluded subjects

A subject will be excluded from the PPS analysis under the following conditions

Code	Condition under which the code is used
900	Invalid informed consent or fraud data
150/1040	Administration of concomitant vaccine(s) forbidden in the protocol
130/1070	Subjects got vaccinated with the correct vaccine but containing a lower volume
140/1070	Vaccination not according to protocol
140/1080	Vaccine temperature deviation
140/1090	Expired vaccine administered
200/2010	Protocol violation (inclusion/exclusion criteria)
230/2040	Administration of any medication forbidden by the protocol
270/2090	Subjects did not comply with blood sample schedule
110/2100	Serological results not available post-vaccination
112/2120	Obvious incoherence or abnormality or error in data

Codes referring to vaccination errors or issues are only applicable to those subjects receiving a booster dose at ad-hoc unscheduled visits.

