5.2.2.2. Right censored Data

Not applicable.

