5.2.2.3. Visit-specific censored Data

Data from visit x will be censored for the PPS analysis under the following conditions.

Code	Condition under which the code is used
270.x/2090.X	Subjects did not comply with blood sample schedule at visit x

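### The SAP's single per-protocol exclusion list, as written, lets a booster dosing error remove a subject who fell below NT 10 from the primary persistence set

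*SAP*

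**What the plan says.** SAP 5.1 defines PP-1 from FAS-1 and PP-2 from FAS-2. Both exclude subjects with a major violation, and both leave its definition to the SAP. SAP 6.3.1 runs persistence on PPS-1 and the booster response on PPS-2.

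SAP 5.2 announces elimination detail set by set, but 5.2.2.1 has a single list that opens "A subject will be excluded from the PPS analysis under the following conditions". It contains:

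- 130/1070, a lower volume than intended
- 140/1070, "Vaccination not according to protocol"
- 140/1080, a vaccine temperature deviation
- 140/1090, expired vaccine
- 110/2100, "Serological results not available post-vaccination"

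A note below the list adds: "Codes referring to vaccination errors or issues are only applicable to those subjects receiving a booster dose at ad-hoc unscheduled visits".

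SAP 5.2.2.2, on right censoring, is marked as not applicable. The only visit-level rule, in 5.2.2.3, is "Subjects did not comply with blood sample schedule at visit x".

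On subjects below 10, Protocol 10.5 and 10.7.2 and SAP 6.3.1 agree: they remain in the persistence analysis in later years with a titre set to 1.

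**The concern.** Two instructions apply to the same people. The retention rule keeps subjects boosted for NT below 10 in the persistence analysis. The exclusion list removes some of them from the set on which that analysis is run. Because the exclusion covers the whole subject, it takes out the valid titre drawn before the booster as well as the later values of 1.

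These exclusions are not neutral. Under SAP 6.2 the booster goes only to subjects whose titre falls below 10, so by plan only persistence failures can acquire a booster code. The percentage at or above 10 by schedule is a primary endpoint, and Protocol 1.2 says the data will guide recommendations on the timing of the second booster. An error that makes persistence look better is the unfavourable direction for that use.

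**Working it through.** **Which set do the codes reach?**

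1. The opening sentence of 5.2.2.1 names the PPS without a number.
2. The note under the list limits which subjects the vaccination codes reach (those boosted), not which set. By plan those are the subjects the retention rule keeps.
3. Neither 5.2.2.2 nor 5.2.2.3 offers a milder treatment for these codes.
4. Protocol 10.4 refers back to the SAP for the definition of a major violation, so it does not settle the matter.

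As written, then, the dosing-error codes act on PPS-1. Code 110/2100 does too if its wording means after the second booster. Protocol Table 5 labels the visits 21 days after the booster that way, but the SAP does not define the term.

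**Direction.** Let n be the group size and s the number at or above 10 at a visit. Removing one subject who is below 10 changes s/n to s/(n − 1), which is higher. At a visit before that subject's failure the change is (s − 1)/(n − 1), which is equal or slightly lower. For example, 48/51 = 94.1% becomes 47/50 = 94.0%.

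**Size.** The documents give no figure to reproduce. Protocol 4.1 says the number falling below 10 cannot be estimated, and no booster deviation rate is given. Group sizes come from Protocol Table 1 (C 51, R 46, AC 103). The number below 10 is assumed to be about 10% of each group.

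| Group | Assumed below 10 | All kept | One excluded |
|---|---|---|---|
| C | 5 | 46/51 = 90.2% | 46/50 = 92.0% |
| R | 5 | 41/46 = 89.1% | 41/45 = 91.1% |
| AC | 10 | 93/103 = 90.3% | 93/102 = 91.2% |

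For group C the Clopper-Pearson 95% intervals are 78.6–96.7 with all kept and 80.8–97.8 with one excluded. With two excluded, 46/49 = 93.9% (83.1–98.7).

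**Approximate average effect.** If a share f is below 10 and a fraction d of those carry an excluding code, the reported percentage is (1 − f)/(1 − f·d). Both f and d are assumed.

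| f | No exclusions | d = 2% | d = 5% | d = 10% | d = 20% |
|---|---|---|---|---|---|
| 0.10 | 90.0% | 90.2% | 90.5% | 90.9% | 91.8% |
| 0.20 | 80.0% | 80.3% | 80.8% | 81.6% | 83.3% |

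**GMT.** It moves the same way at later visits. Assume the 46 persisters in group C have a GMT of 100 and the 5 failures are set to 1. Then 10^(46 × 2/51) = 63.7 with all kept, and 10^(46 × 2/50) = 69.2 with one excluded.

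**Would the FAS analysis show it?** SAP 6.3.1 and Protocol 10.7.1 call for the FAS repeat when at least 10% of subjects with results are excluded in any group. On the planned sizes, exclusions for any reason can reach 5/51 (9.8%), 4/46 (8.7%) and 10/103 (9.7%) without triggering it.

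**The case against.** The strongest reply is that more specific text points to PPS-2. The retention rule in SAP 6.3.1 comes directly before the statement that persistence is analysed on PPS-1. SAP 5.1 defines a major deviation as one "considered to have a significant impact on the immunogenicity result of the subject". A faulty booster dose cannot affect a titre drawn months before it, or later values fixed at 1. The list also resembles a general catalogue of codes: failure to follow the blood-sample schedule appears in it as a whole-subject exclusion and again in 5.2.2.3 as a visit-level one. This stands as evidence of intent. It does not remove the conflict, because the list that would be programmed names neither set.

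Second, SAP 5.1 and Protocol 10.4 promise the FAS as a sensitivity analysis without condition, and FAS-1 needs only one evaluable sample. That is a real safeguard, but SAP 6.3.1 and Protocol 10.7.1 make the FAS analysis conditional, so it is not assured.

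Third, dosing errors should be rare with one centre, a pre-filled syringe, system-allocated treatment numbers and quarantine of stock after temperature excursions. At the assumed 2% to 5% with 10% below 10, the average shift is 0.2 to 0.5 points, against a group C interval about 18 points wide. Comparisons are descriptive (Protocol 10.9, SAP 7) and no test depends on the result. This limits the importance of the point but does not answer it.

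Two stronger readings should be resisted. A reader might infer that 110/2100 can act only on PPS-1, because FAS-2 already requires subjects who "receive one booster dose during the trial and provide one evaluable serum sample after booster dose", which would make the code redundant for PPS-2. But the PP-2 definition itself repeats the post-booster sample, so redundancy shows nothing about where the code acts. A reader might also infer that no rule covers a subject boosted in error at NT 10 or above. On the literal reading 140/1070 already removes that subject from the PPS, and nothing in the documents suggests such errors are expected.

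**Conclusion.** Wrong as written. SAP 5.2.2.1 applies the booster dosing-error codes, and 110/2100 if it refers to the booster, to an undivided PPS. This conflicts with the rule that subjects boosted for NT below 10 stay in the persistence analysis. It is more than a missing label, because the stated rule produces exclusions that depend on the primary outcome.

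For the percentage at or above 10, the bias is upward at and after the failure visit. In the smaller groups one exclusion is worth about 2 points if roughly 10% are below 10, and in AC about 1 point. The actual effect is probably small and may be zero. It depends on how many subjects are boosted, how many of them carry a code, and whether the programmer follows the list or the retention rule. The documents do not show that the sponsor meant to drop failures. PPS-2 is the likely intent for these codes.

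**What to change.** In SAP 5.2.2.1, add a column that assigns each code to PPS-1, PPS-2 or both. For subjects boosted because NT was below 10, apply 130/1070, 140/1070, 140/1080, 140/1090 and 110/2100 to PPS-2 only. State that these subjects stay in PPS-1 with their observed pre-booster titres and the planned value of 1 afterwards. Define post-vaccination in 110/2100.

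Reconcile the unconditional FAS statement (SAP 5.1, Protocol 10.4) with the 10% condition (SAP 6.3.1, Protocol 10.7.1) by always reporting FAS-1 for the primary endpoints.

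The cost is SAP wording, a matching protocol clarification and one extra set of FAS-1 tables. No new data are needed.

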## **4. STUDY COHORT**

### **4.1. Number of subjects/centres**

A total of approximately 200 subjects who participated in study TBEV POLYGELINE FREE (V48)-023 EXT 021 (V48P7E2), who received in a parent V48P7 study one of the following schedules: rapid (R), conventional (C), or accelerated conventional (AC) and a booster vaccination in study V48P7E1 or before study V48P7E1 (only R-schedule) and agreed to participate in this study are to be enrolled.

The number of subjects who will have a decrease of NT antibody titre to below 10 cannot be estimated. There is no information about the kinetics of NT antibodies until 15 years after booster vaccination with *Encepur Adults* available from clinical studies or publications.

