##### **For all subjects:**

- Any investigational or non-registered product (drug or vaccine) other than the study vaccine used during the study period.
- Immunosuppressants or other immune-modifying drugs defined as follows:
  - Systemic administration of corticosteroids (PO/IV/IM) for more than 14 consecutive days within 90 days prior to all blood draws. This will mean prednisone  $\geq 20$  mg/day (for adult subjects), or equivalent. Inhaled and topical steroids are allowed.
  - Administration of antineoplastic and immuno-modulating agents or radiotherapy within 90 days prior to all blood draws.
- Received immunoglobulins or any blood products within 180 days prior to blood draw.
- Administration of long-acting immune-modifying drugs administered at any time during the study period (e.g. infliximab).

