### **10.3. Determination of sample size**

The sample size in this study is determined by the number of eligible subjects still being followed from the original study, V48P7 in a subset of the vaccine groups from that study. In the parent study, sample size for each vaccine group was not based on power calculations, but was considered sufficient when compared with studies using the same vaccine and based on the fact that the primary objective was to be evaluated by summary statistics, not formal hypotheses testing.

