### **10.4. Analysis Sets**

Definition of populations:

- a. All Enrolled Population
- all subjects who:  
have signed an informed consent and have been enrolled
- b. Full Analysis Set-1 (FAS-1)/Modified Intention-to-treat-1 (MITT-1) population, Immunogenicity
- all subjects in the enrolled population who:  
provide at least one evaluable serum sample
- c. Full Analysis Set-2 (FAS-2)/Modified Intention-to-treat (MITT) population, Immunogenicity
- all subjects in the enrolled population who receive one booster dose during the trial and provide at least one evaluable serum sample after booster dose
- d. Per Protocol Set/ Per protocol-1 (PP-1) population, Immunogenicity
- all subjects in the FAS-1/MITT-1 Immunogenicity population who:  
provide evaluable serum samples at the relevant time points and have no major protocol violation as defined in the Statistical Analysis Plan (SAP).
- e. Per Protocol Set/ Per protocol-2 (PP-2) population, Immunogenicity
- all subjects in the FAS-2/MITT-2 Immunogenicity population who:  
provide evaluable serum samples after booster dose and have no major protocol violation as defined in the Statistical Analysis Plan (SAP).

A major deviation is defined as a protocol deviation that is considered to have a significant impact on the immunogenicity result of the subject.

Examples of major deviations would include:

- confirmed exposure to TBE (documented diagnosis of TBE infection) or other Flaviviruses,
- documented TBE or *Flavivirus* vaccination other than indicated during the course of the study.

The main populations for immunogenicity analyses will be the PPS. FAS will be supplied as sensitivity analyses.

Subjects lost to follow up after having received their first booster dose in the V48P7E1 study will not be part of any set of analysis.

f. Safety Population

- The safety population will include all subjects who will receive a booster vaccination in this study.

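### A forbidden drug, a forbidden vaccine or a Flavivirus exposure at any date removes the whole subject from PPS-1, so valid earlier titres leave the primary analysis

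*SAP*

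**What the plan says.** The primary endpoints are "based on the TBE NT antibody levels in serum at year 11, 12, 13, 14 and 15", and the per-protocol set is the main set for them (SAP 5.1 and 6.3.1).

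- **Subject-level codes.** SAP 5.2.2.1 opens with "A subject will be excluded from the PPS analysis under the following conditions". The list includes "Administration of any medication forbidden by the protocol" (230/2040) and forbidden concomitant vaccines (150/1040). Neither entry refers to when the event happened. A note under the table confines codes about vaccination errors or issues to boosted subjects, and it is unclear whether 150/1040 is one of these.
- **Major deviations.** PP-1 admits only subjects without a major violation. The protocol's examples (10.4, repeated almost word for word in SAP 5.1) are "confirmed exposure to TBE (documented diagnosis of TBE infection) or other Flaviviruses" and a TBE or Flavivirus vaccination outside the study plan.
- **Censoring.** The section headed "5.2.2.2. Right censored Data" is marked not applicable. SAP 5.2.2.3 has one visit-level code, for the blood-sample schedule.
- **Drug criteria.** Protocol 6.7.2 ties systemic steroids (with limits on duration and dose), antineoplastic and immuno-modulating agents and radiotherapy to the 90 days before a draw, and immunoglobulins and blood products to the 180 days before a draw. One criterion has no such window: "Administration of long-acting immune-modifying drugs administered at any time during the study period (e.g. infliximab".

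**The concern.** A titre drawn at Year 11 cannot be changed by something that happens after Year 14. Under the SAP, a subject who has such an event between Visits 26 and 27 still loses all five yearly titres from PPS-1, four of them valid. For the time-limited criteria the mismatch runs both ways: the protocol describes an effect on particular draws, and the SAP removes draws before and after the window.

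At stake are valid data in the primary set and its definition: who counts at Year 11 is decided by what happens up to Year 15. There is also a route by which recorded failures could leave the persistence analysis. Protocol 6.7.2 adds vaccine restrictions only for subjects who need a second booster, that is, those already below 10. The SAP has one code list for both per-protocol sets, so a later vaccine in such a subject could remove that failure from PPS-1 as well as from PPS-2.

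**Working it through.** The plan has no figure to reproduce. This study takes the eligible subjects still in follow-up, and for the parent study "sample size for each vaccine group was not based on power calculations". The check is a reading of the rules, then a count under stated assumptions.

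**1. Reading.**

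| Event | Source of exclusion | Dated? | Titres lost from PPS-1 |
|---|---|---|---|
| Forbidden medication | SAP 5.2.2.1, 230/2040 | No | All five |
| Forbidden vaccine | SAP 5.2.2.1, 150/1040 (perhaps boosted only) | No | All five |
| Flavivirus infection, or non-study TBE/Flavivirus vaccine | SAP 5.1, PP-1 | No | All five |
| Draw outside the schedule | SAP 5.2.2.3, 270.x/2090.X | By visit | That visit |

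PP-1 also asks for evaluable samples at the relevant time points. That may be read visit by visit, but the condition on major violations has no date limit. No other section keeps pre-exposure titres in PPS-1.

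**2. Inputs for the count.** Protocol 4.1: "A total of approximately 200 subjects who participated in study". Protocol Table 1: 51 (C) + 46 (R) + 103 (AC) = 200. Five yearly titres give at most 200 × 5 = 1000. This ceiling ignores dropout and the values imputed after a booster. *Assumption, not in the documents:* 2% to 15% of subjects have one lasting exposure, spread evenly over the four between-visit intervals.

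**3. Titres lost.** An exposure in interval j follows j valid titres, j = 1 to 4, mean (1 + 2 + 3 + 4)/4 = 2.5. For m exposed subjects, total loss = 5m, pre-exposure loss = 2.5m, range m to 4m.

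| Exposed | m | Total lost | Pre-exposure lost (range) |
|---|---|---|---|
| 2% | 4 | 20 | 10 (4 to 16) |
| 5% | 10 | 50 | 25 (10 to 40) |
| 10% | 20 | 100 | 50 (20 to 80) |
| 15% | 30 | 150 | 75 (30 to 120) |

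At 5%, the SAP rule leaves 190 subjects at every visit. Right-censoring would leave 200, 197.5, 195, 192.5 and 190 at Years 11 to 15.

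**4. Room below the FAS trigger.** SAP 6.3.1 adds a FAS analysis if at least 10% of subjects with serological results are excluded in any group. Taking the planned group sizes as denominators, the most that can be excluded without triggering it is ceil(0.10 × n) − 1: 5 in C, 4 in R and 10 in AC, 19 in all (9.5% of 200). If all 19 were mid-study exposures, 19 to 76 pre-exposure titres (19 × 2.5 = 47.5 on even timing) would appear in neither analysis.

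**5. Precision.** At about 90% with a titre of at least 10, the Clopper-Pearson width in group C is 18.2 points for 46/51 and 19.9 points for 41/46.

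**6. Recorded failures (hypothetical).** If 10 of 51 in group C are below 10, the rate is 41/51 = 80.4%. If three of those ten leave PPS-1 because of a later vaccine, it becomes 41/48 = 85.4%.

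**The case against.** Much can be said for the plan.

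- **The code table covers less than it seems to.** It has no code for infection, so that part rests on the major-deviation examples. Protocol 6.7.2 restricts other registered vaccines only in subjects who need a booster. A reader might infer that code 150/1040 removes an unboosted subject given a Flavivirus vaccine. The documents do not establish this; such a subject leaves through the major-deviation example in SAP 5.1. This stands as a limit on which rule applies, but the exclusion remains.
- **The protocol is permissive.** Sections 6.7.2 and 6.8 say that these products and conditions may affect evaluability. True, but that leaves the decision to the SAP, and the SAP sets no date limit. For long-acting immune-modifying drugs the protocol criterion is the whole study period, so subject-level exclusion is consistent with it. Censoring from first use is an improvement there, not the correction of a contradiction.
- **FAS-1 keeps the early titres.** It does, so they are not lost to the study, and crossing the 10% trigger would bring them back. It is only a partial remedy: it also keeps post-exposure titres, and SAP 5.1 promises it without condition while SAP 6.3.1 makes it conditional.
- **The stakes are descriptive.** There is no formal comparison (SAP 7), and the precision effect is small. Both points stand.

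A reader might also infer that the primary percentages are biased, or that older and sicker subjects lose more. Neither is shown: the documents give no event rates by age or titre, and 80.4% against 85.4% is a constructed example. Nor would the fix guarantee a complete Year 11. The look-back windows apply to Visit 23 too, and the immunosuppressant exclusions in protocol 4.3 bind only booster recipients.

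**Conclusion.** The point holds as one about discarded valid data and a set definition that looks forward in time. The SAP drops whole subjects from the primary set for events that affect only later titres, or only draws inside a 90- or 180-day window, and it has no censoring rule that could prevent this.

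The size is unknown. Under the assumed 2% to 15% of subjects with one lasting exposure, evenly timed, 10 to 75 pre-exposure titres of at most 1000 are lost on average; at 5% the figure is 25 (10 to 40). The count models right-censoring of lasting exposures only, not the time-limited windows. The documents do not support a claim of material loss of precision or demonstrated bias. This is a cheap improvement worth making before the final analysis, not a threat to the trial's conclusions.

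**What to change.** 1. **SAP 5.2.2.2.** Replace the present entry with a rule for PPS-1: titres are right-censored from the date of a documented TBEV or other Flavivirus infection, a TBE or Flavivirus vaccination other than the study booster, or the first on-study dose of a long-acting immune-modifying drug. Earlier titres are kept.
2. **SAP 5.2.2.3.** Add visit-specific censoring for draws that fall in the windows exactly as protocol 6.7.2 defines them, including its limits on steroid route, duration and dose and its allowance for inhaled and topical steroids. This may also censor Visit 23.
3. **Imputation.** State that titres censored for exposure are not refilled under protocol 10.5, which otherwise replaces a non-evaluable value by the lower of its neighbours. State also that a subject already recorded below 10 stays in PPS-1 with NT = 1 for later years despite a later exposure.
4. **Codes by set.** Apply the booster-related vaccine and vaccination codes to PPS-2 only.

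The cost is SAP text and visit-level elimination codes, and a PPS-1 size that differs by year. One check is needed first: protocol 6.7.1 itemises on-study vaccinations only for booster subjects or in relation to an SAE, although Table 4 has a general recording row. The sponsor should confirm that vaccination dates are captured for unboosted subjects too.
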